Variables that will be included in this analysis are data collected at the patient's initial clinic visit: DHPG, *SLC6A2* genotype, ADHD subtype, ADHD severity, co-morbid anxiety or oppositional defiant disorder, age, and gender. Predictive power of classification models will be assessed by computing the area under the receiver operating characteristic curve and/or by k-fold cross-validation. Two-sample t-tests or non-parametric alternatives will be utilized to test for group differences in percent decrease in DHPG and a differences in proportions test will be used to assess the association between response and *SLC6A2* genotype. In addition, global metabolomic analyses will be conducted to determine whether non-responders and responders are intrinsically different in their biochemical make-up. This will further understanding of how differences in

response phenotype could be a result of different biological pathway involvement in ADHD. Digital maps will be constructed for partial least square-discriminant analysis (PLS-DA) models with prior knowledge of which volunteers were categorized as responders and non-responders. The variable influence on the projection (VIP) parameter will be used to identify which metabolites (i.e. pathways) are the most predictive of differentiating between the responder and non-responder populations. Analyses will also be conducted to determine mechanistic reasons for why certain individuals are non-responders or responders. Changes in pharmacodynamic endpoints will be compared between responders and non-responders. Specifically pharmacodynamic parameters such as  $I_{max}$ ,  $IC_{50}$ , differences in pupil diameter changes in localizations and discrimination tasks, and overall change in DHPG will be compared between the two populations using MANOVA and/or appropriate two-sample test.

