ATX pharmacodynamic data for each *SLC6A2* activity group will be examined using standard descriptive statistics. Analysis of variance will be used to compare parameters between pre-defined genotype populations followed by application of the appropriate parametric or non-parametric post-hoc test to determine where inter-group differences occur. Linear and non-linear least squares regression analysis will be used to examine the correlation between DHPG fitted parameters and changes in eye-tracking and pupillometry differences in *SLC6A2* genotype groups. Univariate analysis of variance, nonlinear regression and analysis of covariance will be used to evaluate the relationship between demographic variables (alone or in combination) with corresponding pharmacodynamic parameter estimates. All analyses will be performed in SPSS version 11.5 (SPSS, Chicago, IL) with the significance limit set at  $\alpha=0.05$ . A sample size of 120 was deemed reasonable with the volume of patients being referred to the ADHD sub-specialty over a four year period. Powering of statistical tests was done assuming 20% attrition and data simulated for 96 patients. Assuming that 30% of the participants completing the study are categorized as responders, an  $\alpha = 0.05$ , and power = 80%, a mean difference in covariates assessed of 0.6 standard deviations is detectable with a one-sided t-test. With zero attrition, the mean detectable difference in covariates of interest drops to 0.5 standard deviations.

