## 20.2 Sample Size Determination

We hypothesize that there are at least two discrete ATX response phenotypes groups and additionally that these groups may be distinguished by differences in pharmacodynamic markers, and/or baseline patient characteristics. We will use two-sample *t*-tests (if transformed data are approximately Gaussian) or appropriate non-parametric alternatives to test for group differences in baseline and maximal change in DHPG, and a difference in proportions test to assess association between response group and SLC6A2 genotype. To estimate power for these tests we assumed 20% attrition and simulated data for 96 patients. For a 30% response rate among study completers (a conservative estimate),  $\alpha = 0.05$ , and power = 80%, a mean difference of 0.6 SDs between responders and non-responders (eg, on DHPG) was detectable using a one-sided *t*-test. With 120 patients (zero attrition) a 0.5 SD difference was detectable. Depending on the rate and nature of attrition and missing data we will consider non-response weighting or data imputation to reduce estimation bias and improve power. We assessed power for the difference in proportions test based on a 45% probability of a given patient having at least one SLC6A2 lower expression “T” allele (*i.e.*, frequency of SLC6A2 -3081 AT and TT genotypes ~45% based on a minor T allele frequency of 0.061

([http://useast.ensembl.org/Homo\\_sapiens/Variation/Population?db=core;g=ENS G00000103546;r=16:55655604-55706192;v=rs28386840;vdb=variation;vf=109832868](http://useast.ensembl.org/Homo_sapiens/Variation/Population?db=core;g=ENS G00000103546;r=16:55655604-55706192;v=rs28386840;vdb=variation;vf=109832868))).

Assuming attrition of 20% and a response rate of 30%, power was 81% to detect a 0.23 difference in allele frequency between responders and non-responders using a one-sided test. With 120 patients a 0.20 difference was detectable with 80% power.

While these analyses are central to our hypothesis, we recognize that other plasma metabolites or genetic differences may contribute to varying drug response. A target metabolite panel will be assayed in each participant and statistical analyses of these will be analogous to DHPG. A panel of genetic variants will also be analyzed for contribution to variable drug pharmacokinetics, pharmacodynamics, and clinical response in the same manner as the SLC6A2 variant described above.

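### The plan lets the responder classifier be judged on its own fitting data, requires no validation of the PLS-DA metabolite ranking, and states no error limit across the metabolite and variant panels

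*Combined protocol and SAP*

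**What the plan says.** Section 20.1 (Clinical Outcomes) builds a model separating responders from non-responders on baseline DHPG, SLC6A2 genotype, ADHD subtype and severity, co-morbid anxiety or oppositional defiant disorder, age and gender. Its performance rule is: "Predictive power of classification models will be assessed by computing the area under the receiver operating characteristic curve and/or by k-fold cross-validation". The data from which the AUC is computed are not named.

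The same section fits partial least squares discriminant analysis (PLS-DA) "models with prior knowledge of which volunteers were categorized as responders and non-responders". It continues: "The variable influence on the projection (VIP) parameter will be used to identify which metabolites (i.e. pathways) are the most predictive". It gives no number of components, VIP cut-off, permutation test or hold-out set.

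On the panels, Section 20.2 will "test for group differences in baseline and maximal change in DHPG", and adds: "A target metabolite panel will be assayed in each participant and statistical analyses of these will be analogous to DHPG". A panel of genetic variants is to be handled in the same way as SLC6A2. Section 4.1 (Secondary Study Endpoints) puts the metabolite panel at about 30, and the example list in Appendix I has 31 entries including DHPG.

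Three sentences bear on error control:
- At the end of the SLC6A2 genotype-group paragraph: "All analyses will be performed in SPSS version 11.5 (SPSS, Chicago, IL) with the significance limit set at" 0.05.
- In the same paragraph, an unnamed test after analysis of variance, "followed by application of the appropriate parametric or non-parametric post-hoc test to determine where inter-group differences occur".
- In the responder comparison, pupil measures, fitted parameters and "overall change in DHPG will be compared between the two populations using MANOVA and/or appropriate two-sample test".

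**The concern.** The classifier and PLS-DA serve the secondary objective on baseline differences between responders and non-responders (Section 2.1) and Hypothesis 3 (Section 2.2). An AUC taken from the fitting data is biased upward, because the model has already been tuned to those labels. With few responders and several covariates the bias is large enough to look like modest prediction. PLS-DA is more exposed, since it has about 30 predictors and is built to separate labelled groups. VIP will always rank some metabolites first, whether or not any is related to response.

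The panel tests raise a separate problem. When tens of comparisons share no stated error limit, some will look positive by chance, and the plan does not tell a reader how to weigh them. The risk is that noise is reported as a predictor of atomoxetine response.

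**Working it through.** **Inputs from the documents.** Section 20.2 assumes 96 patients after 20% attrition from 120, 30% responders and alpha 0.05, with one-sided tests. 0.30 × 96 = 28.8, so 29 versus 67. At 120 patients, 0.30 × 120 = 36, so 36 versus 84. Section 20.1 lists 7 covariates, or 8 if anxiety and oppositional defiant disorder count separately.

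**The plan's own figure.** Noncentrality = d / √(1/n₁ + 1/n₂). For 29 versus 67, √(0.03448 + 0.01493) = 0.2223, so d = 0.6 gives 0.6 / 0.2223 = 2.70. One-sided power is 85%, and the difference detectable at 80% power is 0.557 SD. For 36 versus 84 it is 0.498 SD. These agree with the stated 0.6 and 0.5 SD to one decimal.

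**Classifier on pure noise.** A linear discriminant was fitted to independent normal covariates unrelated to response, in 2,000 simulated datasets at 29 versus 67:

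| Covariates | Fitting-data AUC, mean (5th–95th percentile) | 5-fold cross-validated AUC, mean (5th–95th percentile) |
|---|---|---|
| 7 | 0.661 (0.587–0.740) | 0.498 (0.334–0.640) |
| 8 | 0.674 (0.602–0.748) | 0.502 (0.343–0.646) |

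A more favourable case takes no attrition and the 47% response cited in Section 3.1. 0.47 × 120 = 56.4, so 56 versus 64, and the fitting-data AUC still averages 0.63 to 0.64.

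**PLS-DA on pure noise.** With 30 metabolites, 29 versus 67 and 1,500 datasets per setting, the mean fitting-data AUC was as follows. Correlations and component numbers are assumptions, since the documents give none.

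| Correlation between metabolites | 1 component | 2 components |
|---|---|---|
| 0 | 0.807 | 0.841 |
| 0.3 | 0.718 | 0.813 |
| 0.5 | 0.665 | 0.812 |

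The cross-validated mean was 0.499 to 0.504 throughout. With independent noise metabolites, about 10 of 30 exceed VIP = 1. That cut-off is also assumed.

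**Panel tests.** Appendix I gives 31 − 1 = 30 metabolites besides DHPG. One test each makes 30 tests; testing both baseline and maximal change makes 60. The count rises if the fitted parameters that Section 20.1 estimates for every neurotransmitter are also compared, or if variants are added. Suppose each is tested at 0.05 with all nulls true:
- Expected false positives: 30 × 0.05 = 1.5 and 60 × 0.05 = 3.0, whatever the correlation.
- Chance of at least one if independent: 1 − 0.95³⁰ = 0.785 and 1 − 0.95⁶⁰ = 0.954.
- At assumed correlations of 0.3, 0.5 and 0.7, one-sided: 0.53, 0.40, 0.28 (30 tests) and 0.66, 0.50, 0.34 (60 tests).
- The same, two-sided: 0.66, 0.51, 0.34 (30 tests) and 0.85, 0.66, 0.43 (60 tests).

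**Whether existing text supplies the control.** The post-hoc test compares SLC6A2 genotype groups. The MANOVA is optional, is paired with an alternative, and concerns pharmacodynamic endpoints between response groups. Neither limits error across the metabolite or variant panels.

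**The case against.** Several counter-arguments have force.

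- **The AUC.** The plan does not say it will come from the fitting data, and it names cross-validation. A reader might infer that in-sample assessment is the chosen method. The text supports only that it is permitted.
- **PLS-DA.** A reader might infer that no validation is contemplated. PLS-DA is a classification model, so the sentence on classification models may cover it, in which case k-fold cross-validation is named but optional. If that sentence does not cover it, the plan nowhere promises an AUC for PLS-DA, and the PLS-DA figures above apply only if one is reported. On either reading, validation can be skipped and VIP selection has none.
- **The 0.05 limit.** A reader might infer that the plan runs the panel tests at 0.05. The sentence setting that limit is tied to SPSS and closes the SLC6A2 paragraph, while Section 20.1 assigns the response analysis to SAS and R. In Section 20.2, 0.05 is only a power input. What stands is that no limit is stated for the panels.
- **Exploratory intent.** Section 4.1 speaks of exploring baseline characteristics, and Section 20.2 ranks DHPG and SLC6A2 as central, ahead of other metabolites and variants. This lowers the weight of the point. Against it, Hypothesis 3 is listed among hypotheses to be tested, and nothing says that panel results will be treated as hypothesis-generating only.
- **The remedy.** A particular false-discovery level is a trade-off, not a necessity.

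**Conclusion.** The concern holds as a gap in what the plan requires. The plan does not commit to a wrong method. The wording admits a fitting-data AUC that averages 0.66 to 0.67 on noise at 29 versus 67 (0.63 to 0.64 at an assumed 56 versus 64), where the honest value is 0.50. If an AUC were reported for PLS-DA on 30 noise metabolites, it would average about 0.66 to 0.84 under the assumed correlations (0 to 0.5) and 1 or 2 components. No error limit across the panels is stated; the 1.5 to 3.0 expected false positives are conditional on testing each metabolite at 0.05.

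The simulations assume normal covariates and a linear classifier, so the exact values would shift with the real data, although the upward bias would remain. It would be wrong to extend the point to the pre-named DHPG and SLC6A2 tests: it concerns secondary analyses and leaves those tests untouched.

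**What to change.** 1. Replace the and/or wording so that every reported AUC is validated by repeated k-fold cross-validation or bootstrap optimism correction, with any variable selection inside the resampling, and is given with an interval. Repetition matters because a single 5-fold AUC on noise spans about 0.33 to 0.65 (5th to 95th percentile).
2. For PLS-DA, choose the number of components by cross-validation, report a label-permutation p-value beside any VIP ranking, and call the ranking exploratory if the model does not beat permutation.
3. Keep 0.05 for the pre-named DHPG and SLC6A2 tests. Label the other metabolites and variants exploratory, with effect sizes and intervals, and preferably false-discovery q-values within each panel.

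The work is SAP wording and a little computing; no visits or samples change. Reported AUCs will be lower and imprecise. Optional q-values also cost power. The table takes Benjamini-Hochberg at 10% over 60 independent tests, with 3 to 6 true effects, at 29 versus 67. One-sided is the plan's own basis for power.

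| True effect | One-sided power, unadjusted → adjusted | Two-sided power, unadjusted → adjusted |
|---|---|---|
| 0.6 SD | 85% → about 48–58% | 76% → about 38–46% |
| 0.8 SD | 97% → about 82–89% | 95% → about 76–83% |

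In return, the false share of discoveries (two-sided) falls from 30–52% to about 9%.

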## 4.0 Study Endpoints and Rationale

### 4.1 Primary Study Endpoints

The primary aims of this study focus on characterizing the relationship between changes in pharmacodynamic markers and clinical outcome measures, when inter-subject variability in ATX pharmacokinetics has been minimized (Fig. 3). ATX pharmacodynamics will be measured using plasma DHPG and metabolomic data, pupillometry during attention tasks, and changes in blood pressure and heart rate. Clinical outcomes will be assessed by standardized ADHD measures used in a clinical setting, of which include: NICHQ Vanderbilt Assessment Scale (ADHD symptom rating scale); Strengths and Difficulties Questionnaire; Child Behavior Checklist; the School Intervention Questionnaire; Medication Side Effects; and Clinical Global Impression. Some of these questionnaires will also capture comorbidity information, such as Oppositional Defiant Disorder (ODD). We will also use the Kiddie Schedule for Affective Disorders and Schizophrenia for School-Age Children – Present and Lifetime Version (K-SADS-PL) or K-SADS-COMP (the computerized version of the K-SADS-PL) to diagnose ADHD and commonly associated comorbidities. The K-SADS-PL is a semi-structured interview that is extensively used in clinical psychology research to diagnose an extensive array of psychopathology based on the DSM-5. Given the length of this interview, common research practices are to select only the modules that are expected to be pertinent to the study participant (Black et al., 2012; Kariuki et al., 2018; Caudle et al., 2020). The K-SADS-PL modules selected for this research study are as follows: agoraphobia, separation anxiety disorder, social anxiety disorder/selective mutism, specific phobias, generalized anxiety, obsessive compulsive disorder, and post-traumatic stress disorder. The other research comorbidities or impairments that we will assess for and associated psychometric tests we will use are as follows: impairment in executive function using the Behavior Rating Inventory of Executive Function (BRIEF); anxiety using the Screen for Child Anxiety and Related Disorders (SCARED); intelligence quotient using the Kaufman Brief IQ Test (KBIT); and sluggish cognitive tempo using the Barkley Sluggish Cognitive Tempo Scale (SCT). Pharmacodynamic data will be obtained: baseline (Research Visit 1); when ATX is first initiated in a participant with the first dose (Research Visit 2); when the participant has taken the medication chronically and thus, expected to be at steady-state (Research Visit 3); and at the end of study when the dose has been optimized for the participant (Research Visit 4). Concurrent pharmacokinetic analysis will take place to ensure that ATX plasma and urine exposure variability has been minimized using methods described in a previous ATX pharmacokinetic study conducted at Children's Mercy Hospital (Brown et al., 2016). Additionally, we will measure ATX and metabolites in sweat as surrogate for fraction of drug unbound (Marchei et al., 2012; Marchei et al., 2013). The clinical ADHD questionnaires will be administered at the Intake Visit and at follow-up visits following initiation of atomoxetine treatment (6-weeks, 12-weeks, and

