## 5.0 Study Intervention/Investigational Agent

### 5.1 Description

ATX is a norepinephrine reuptake transporter inhibitor which is approved by the FDA for use in children with ADHD. The medication displays high inter-individual pharmacokinetic variability, which has been associated with *CYP2D6* genotype. An individual's predicted *CYP2D6* phenotype can be estimated from their genotype. This estimation is quantified as a *CYP2D6* activity score (AS). The *CYP2D6* predicted phenotype and the participant's height, weight, habitus, and gender are used to inform the ATX dosing tool, the individualized genetic and ontogeny pharmacokinetic model (iGO-PK). Both the *CYP2D6* genotype-predicted phenotype activity score and iGO-PK are described below. Doses that are expected to result in  $C_{max,ss}$  values of 400 ng/mL, 600 ng/mL, and 800 ng/mL will be calculated for each participant. Study physicians will start with a dosing regimen that is predicted to achieve a  $C_{max,ss}$  of 400 ng/mL and will titrate the dose to reach  $C_{max,ss}$  values of 600 ng/mL or 800 ng/mL according to participant response. Study physicians may choose to titrate slowly to  $C_{max,ss}$  of 400 ng/mL when initiating ATX therapy to avoid side effects.

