#### *iGO-PK Model*

This method was developed using data generated from a previous ATX single-dose PK study conducted at Children's Mercy Hospital (Brown et al., 2016). This model stratifies participants into two distinct populations: individuals who are CYP2D6 PM and those who non-PMs, i.e. IM, EM1, EM2, and UM (read above for more details on *CYP2D6* genotype and phenotype prediction). With the new changes to *CYP2D6* genotype-to-

phenotype interpretation and study design, the only major change is that children with two reduced function alleles will be modeled as an IM. Analysis of the previous PK study found that in non-PM participants, the dose-exposure relationship was best described using a two-compartment model with first order absorption and first order clearance. In PM participants, dose-exposure was best described using a one compartment model with first order absorption, first order clearance, and a secondary peaking component. Additionally, lean body weight (LBW) and obesity status (positive or negative) variables were found to significantly impact variability in ATX exposure in both models.

Retrograde extrapolation of an initial dose of ATX for PK Study 1 will be determined by setting the desired  $C_{max}$  goal at steady-state ( $C_{max,ss}$ ) to 400 ng/mL, and incorporating patient specific parameters CYP2D6 AS, LBW, and obesity status. The actual dose dispensed will be as close as possible to the model generated dose, given the available atomoxetine capsule formulations. Additionally, we will also consider the most convenient combination of capsules for a child to take and how a prescriber would dose this medication in a naturalistic setting. During the course of the study, we will also be monitoring clinical response and toxicity. The exposure ( $C_{max,ss}$ ) may be titrated down to below 400 ng/mL to reduce toxicity or up to 800 ng/mL to increase response as tolerated.

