18-Week Visit with Study Physician – The participant and family meet with a study physician approximately 6 weeks after the 12-Week Visit with Study Physician. A ± 2-week window is allowed for ease of scheduling. Prior to this visit, questionnaires will be sent out via CHADIS to parents and teachers to assess participant's behavior. During this visit, safety, efficacy, and side effects will be assessed and dose adjustments will be made accordingly. In addition, baseline questionnaires will be re-administered to gauge symptom and impairment changes post-treatment initiation. Dose adjustments may be outside research and visits with study physicians as needed.

Research Visit 4 – This visit is also referred to as pharmacokinetic study 3 (PK3) or end of study PK. This vist occurs after the 18-Week Visit with Study Physician. This visit takes place in the PCRU and consists of the same procedures as Research Visit 3. Determination of Study Design will be confirmed prior to visit, as some participants may require switching to a different study design if frequency of dosing has changed. During this visit, baseline psychometric measures will be re-administered to measure change post-treatment initiation. An end of study EKG will be obtained, and a Dietary Survey Questionnaire will be administered.

- Description of Research Procedures

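### Dose is titrated on response, but the responder versus non-responder contrasts of DHPG change and pupil change name no visit and carry no exposure term

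*Combined protocol and SAP*

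**What the plan says.** **Exposure.** Section 4.1 frames the primary aims for the situation "when inter-subject variability in ATX pharmacokinetics has been minimized". Section 5.1 starts every child at a dose predicted to give a Cmax,ss of 400 ng/mL, then titrates to "values of 600 ng/mL or 800 ng/mL according to participant response". Under iGO-PK Model it adds that exposure "may be titrated down to below 400 ng/mL to reduce toxicity or up to 800 ng/mL to increase response as tolerated".

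**Visits.** Pharmacodynamic data are collected at baseline, after the first dose (Research Visit 2), at steady state (Research Visit 3) and at Research Visit 4, "at the end of study when the dose has been optimized for the participant". Section 11.1 says of Research Visit 4: "This vist occurs after the 18-Week Visit with Study Physician".

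**Contrasts.** In the Clinical Outcomes part of 20.1, t-tests or non-parametric alternatives are used to "test for group differences in percent decrease in DHPG". Later, after Imax and IC50 are listed, "differences in pupil diameter changes in localizations and discrimination tasks, and overall change in DHPG will be compared between the two populations using MANOVA" or a suitable two-sample test. Section 20.2 uses two-sample tests "to test for group differences in baseline and maximal change in DHPG" and bases power on them. None of these sentences names a visit, a dose, Cmax or AUC.

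**Confounders.** For markers against response, 20.1 names only adherence. Section 11.2 (Research Visit 4) defines adherence as the share of scheduled doses taken.

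**The concern.** These contrasts serve Primary Objective 2 and Hypothesis 2. Section 3.2 argues that target-level effects cannot be studied unless exposure variability is first minimised. Titration on response brings an exposure difference back, and it does so between the two groups being compared. One non-responder category in 20.1 consists of children who stop for lack of efficacy despite escalation, so the plan itself expects some non-responders at higher targets.

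A higher target lowers DHPG further, whatever the state of the transporter. If non-responders end at higher exposure, a genuinely greater sensitivity in responders would be masked. If responders end higher, a difference could appear where there is none. Adherence does not help: a fully adherent child at a 400 target and one at an 800 target get the same score.

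For pupil size the direction cannot be predicted, because 4.1 describes a U-shaped relation between norepinephrine release and task performance.

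**Working it through.** **1. The plan's own figure.** Section 20.2 assumes 96 patients, 30% responders, one-sided alpha 0.05 and 80% power, and gives 0.6 SD. With 29 v 67, the detectable difference is (1.645 + 0.842) × √(1/29 + 1/67) = 2.487 × 0.2223 = 0.55 SD, which rounds up to 0.6. Power at exactly 0.6 SD (noncentral t, 94 df) is 85%. With 36 v 84 of 120 it is 0.50 SD, as stated. These figures reproduce; they assume that the groups are compared at like exposure.

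**2. Which visits are exposed to the problem.**
- Research Visit 2: first dose, common 400 target. Not affected.
- Research Visit 3: 11.1 and the Schedule of Events place the 6-week visit after it, so it often precedes a response-based change. They also allow it at any time up to the 18-week visit, and 11.2 allows dose changes for lack of efficacy before week 6. Sometimes affected.
- Research Visit 4: after titration. Affected.

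**3. Size for DHPG.** The documents give no IC50, no between-child variability and no exposure by response group, so everything below except n, alpha and 0.6 SD is assumed.
- Exposure: C = target × exp(N(0, 0.30)).
- Fractional effect: f = C/(IC50 + C).
- Suppression = (1 + CV·z + shift) × f, where shift = 0.6 × CV in responders and 0 in non-responders. The tested direction is greater suppression in responders.
- Small imbalance, shares at 400/600/800: responders 50/30/20%, mean 0.5×400 + 0.3×600 + 0.2×800 = 540; non-responders 35/30/35%, mean 140 + 180 + 280 = 600.
- No imbalance: 40/30/30% in both groups.

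Hand check at IC50 400, ignoring variability around the target: f is 0.500, 0.600 and 0.667 at the three targets. Mean f is 0.563 in responders and 0.588 in non-responders, and 0.581 overall. Bias = 0.025/(0.30 × 0.581) = 0.14 SD against responders.

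Simulated raw one-sided power at CV 30% (nominal 85%):

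| IC50 (ng/mL) | 50 | 200 | 400 | 800 |
|---|---|---|---|---|
| Same dose spread, no imbalance | 84% | 80% | 72% | 63% |
| Small imbalance | 81% | 66% | 51% | 36% |
| Loss due to response-driven titration (points) | 3 | 14 | 21 | 27 |

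The gap between 85% and the first row comes from dose spread alone and is not part of this point. As a cross-check, a pure shift of 0.1 or 0.2 SD against a true 0.6 SD takes power from 85% to 73% or 56%, a loss of 12 or 29 points. That is in line with the table, since the small-imbalance bias at CV 30% runs from 0.03 to 0.20 SD.

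**4. Range.** Small-imbalance bias at CV 60% is 0.01–0.10 SD. A moderate imbalance (mean target 510 v 660) gives 0.07–0.48 SD at CV 30%.

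**5. Opposite direction.** With responders at 600 v 540 and no true effect, the raw one-sided false-positive rate at CV 30% is 7.0/10.5/13.9/17.6% over the same IC50 values.

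**6. With adjustment.** Adding log measured exposure as a covariate gives power of about 79–83% in the small-imbalance case at CV 30%, and a false-positive rate of about 5–6% in the opposite case.

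**The case against.** - *The dosing algorithm equalises exposure.* It does so at a given target. It does not remove a deliberate two-fold range of targets chosen by response.
- *Exposure is handled elsewhere.* This is true and deserves credit. Secondary Objective 1 relates exposure, transporter inhibition and response; 20.1 models DHPG on concentration and regresses pupil data on Cmax and AUC; Imax and IC50, which are conditional on concentration, are compared in the same sentence as the raw changes. None of this enters the raw contrasts, and nothing ranks Imax/IC50 above them. Nor is Imax/IC50 wholly free of the feature: escalated children contribute more exposure levels, so precision may differ by group.
- *The affected visit may not be the one used.* Sections 8.2 and 20.1 count participants without Research Visit 4, and Research Visit 3 normally comes before the 6-week visit. This limits the reach of the point, but no visit is excluded, so it does not settle it.
- *The raw association is of interest in itself.* Hypothesis 2 is not stated conditionally on exposure, and achieved inhibition may be part of how exposure affects response. This stands: the raw contrast should not simply be replaced.
- *The size is assumed.* This also stands. The model is static and ignores the delayed DHPG response that 20.1 plans to model.

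A reader might infer that the whole fall from 85% to 36% is the cost of titration, or that the Hypothesis 2 analysis is invalid. The documents support neither. Part of that fall is dose spread, and baseline DHPG, genotype and first-dose contrasts are untouched.

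**Conclusion.** The gap in specification is certain. At a post-titration visit the raw DHPG and pupil contrasts compare groups whose exposure was set partly by the outcome, and the plan neither names the visit nor adjusts for it. The size cannot be fixed from the documents and runs from negligible to large, depending on IC50, between-child variability and how far titration differs by group. For DHPG the bias is probably towards the null. That is not certain, because down-titration is allowed and a child who responds at 600 or 800 ng/mL counts as a responder. For pupil neither size nor direction can be given. The stated 0.6 and 0.5 SD are not wrong on this account. This is a cheap improvement to the analysis plan.

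**What to change.** In 20.1 and 20.2:

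1. Name the visit for each DHPG and pupil contrast.
2. For Research Visits 3 and 4, add a regression or mixed model of marker change on response group with measured same-visit exposure: Cmax,ss, or AUC over the dosing interval. Allow a non-linear exposure term for pupil, as 20.1 already does in its exposure regressions.
3. Base the target-level conclusion on that model or on the planned Imax/IC50 comparison, and say in advance which.
4. Keep the raw contrast, labelled as descriptive and unadjusted for exposure.
5. Report the Research Visit 2 contrast as a pre-titration sensitivity analysis.

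The Schedule of Events already has pharmacokinetic blood samples at Research Visits 2, 3 and 4, so no patients, procedures or dosing changes are needed. The cost is SAP wording and slightly more analysis. The adjusted estimate leaves out any part of the association that acts through exposure, which is why both results are reported.
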